- Results of 12 month surveillance biopsies
- Lipid panels and use of lipid lowering medications at 1 year after transplant
- Incidence of MI and CHF at 1 and 3 years after transplant

- Incidence of wound infection at 1 year after transplantation
- Incidence of lymphocele at 1 year after transplantation
- Plasma concentrations of S-adenosyl homocysteine (SAH) and S-adenosyl methionine (SAM) Plasma concentrations of endothelial dysfunction markers (symmetric and asymmetric dimethyl arginine (SDMA, ADMA), L-arginine, L-citrulline, L-ornithine, cysteine, and homocysteine over the observation period
- Plasma concentrations of bioactive lipids (HODEs, HEPEs, HETEs, and prostaglandins) over the observation period
- Plasma protein patterns

Data analysis: The incidence of graft loss, patient death, and acute rejection will be compared by chi squared analyses. Patient and graft Kaplan-Meier survival curves will be compared by log rank test. We hypothesize there will be no statistically significant difference between the treatment arms. As this is a pilot study, it was not statistically powered to detect subtle differences in outcome. All continuous variables such as serum creatinine, cGFR, serum lipids, WBC, platelets, etcetera will be compared by student's t test. Any other dichotomous variables will be compared by chi squared analysis.

1 Background

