3.3 Exploratory objectives

4 To explore the kidney and vascular endothelial function assessed by a panel of molecular markers over the observation period. Study design

Randomized, single center parallel-group, open-label study.

Pilot study with exploratory objectives.

Eligibility: All primary or retransplant recipients of deceased donor or living donor grafts with negative crossmatch who are felt to have good expectations for renal function recovery after surgery will be offered entry into the study.

Treatment scheme is as described above, with Solumedrol 500 mg IV in OR as induction, then 5 doses of Thymoglobulin starting morning of POD 1 at 1.25 mg/dose (rounded to nearest 25 mg) with rapid steroid taper over five doses. The mTOR inhibitor drug will be started on POD 0 and Neoral introduced as renal function recovers, usually starting on POD 2.

Measurement/Assessments: as described above, graft and patient survival per standard definitions, clinically indicated biopsies for determination of acute cellular or antibody mediated rejection, renal function as estimated from serum Cr based on MDRD, clinic visits for wound assessment, standard of care labs for renal function, bone marrow function (WBC and platelet count), liver function, lipid panel, donor specific antibody determination during any significant increase in serum Cr, drug levels routinely monitored for need of number of dose adjustments and compliance, Emergency Room and hospitalizations, as well as unscheduled clinic and other physician visits. For the pilot study, we would perform scheduled CMV, EBV and serum BK PCRs monthly for the first year, then quarterly or with any viral symptoms.

A subset of patients will have coded plasma samples sent to clinical research and development at the University of Colorado. These biomarker samples will be used to assess vascular endothelial dysfunction and inflammation markers as well as kidney dysfunction markers.

Plasma samples are collected and stored at The Ohio State University Wexner Medical Center tissue typing lab per standard of care.

5 Population

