7.1 Table 7-1

Assessment schedule:

Visit number	1 Screening/ Baseline	2	3	4	5	6	7	8	9	10	11	12	13	14	15	16	17	18
Time of Visit		Day 0	Day 1	Day 2	Day 3	Day 4	Day 5 ¹	Day 6 ¹	Day 7 ¹	Wk 2	Mo 1	Mo 2	Mo 3	Mo 6	Mo 12	Mo 18	Mo 24	Mo 36
Inclusion/Exclusion criteria	X																	
Informed consent	X																	
Physical examination	X	X	X	X	X	X	X	X	X	X	X	X	X	X	X	X	X	X
Demographics	X																	
Medical History	X																	
Pregnancy Test ²	X																	
Vital signs	X	X	X	X	X	X	X	X	X	X	X	X	X	X	X	X	X	X
Hematology		X		X				X	X	X	X	X	X	X	X	X	X	X
Chemistry		X			X			X	X	X	X	X	X	X	X	X	X	X
Lipid panel	X									X	X	X	X	X	X	X	X	X
24 hour urine												X	X	X	X	X	X	X
Alloscreen	X															X		
Flow Crossmatch	X															X		
HGB A1C																X		X
Kidney Biopsy	X															X		
Adverse events		X	X	X	X	X	X	X	X	X	X	X	X	X	X	X	X	X
Cyclosporine level ³				X				X	X	X	X	X	X	X	X	X	X	X
Everolimus level ³					X			X	X	X	X	X	X	X	X	X	X	X
Optional sub study: Plasma for Biomarkers ⁴	X				X			X	X	X	X	X	X	X	X	X	X	X

Legend:

- 1: If still inpatient
- 2: Females capable of childbearing
- 3: Cyclosporine and Zortress levels are monitored twice weekly for 0-3 months post-transplant, every two weeks for 3-12 months post-transplant, and monthly greater than 1 year post-transplant.
- 4: Plasma for biomarkers will be assessed at the University of Colorado in a subset of patients using existing plasma samples.

Patients will be followed as per the standard of care at this transplant center (The Ohio State University Medical Center, Division of Transplantation). Additional study procedures include a protocol biopsy at month 12 and some additional laboratory work at screening/baseline and at months 6, 12, 24, and 36.

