10.1.2 Statistical hypothesis, model, and method of analysis

The primary endpoint will be a composite endpoint of graft survival (non-death censored) and biopsy proven acute rejection at 1 year.

Secondary endpoints at 6 months, 1, 2 and 3 years will include: graft survival and patient survival/death at 2 and 3 years, rate and grade of acute cellular rejection, rate of acute antibody mediated rejection, rate of new donor specific antibody formation, estimated CrCl by MDRD, lipid control as determined by requirement for anti-lipid medications and average levels with and without medications, ability to maintain initial immunosuppressive medications and reason for switch if required, wound complications as determined by need for wound packing, infection treatment with antibiotics, presence of hernia on exam and requirement for hernia repair, as well as presence of symptomatic lymphocele, and New Onset Diabetes After Transplant as determined by need for new oral or sustained Insulin medication.

Statistical analysis will be performed on SPSS or STATA software with dichotomous variables evaluated by Chi-Squared analysis, continuous variables by Student's T-Test, non-parametric outcomes will be assessed by Wilcoxon rank sum test (Mann-Whitney U test). Kaplan-Meier survival curves with log rank tests will be used to determine a difference in graft and patient survival over time.

Safety data will include patient and graft survival, biopsy proven acute rejection, and hospital admissions.

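### For plasma markers sampled at up to 13 visits, the plan states only two-sample tests and names no time point, per-patient summary or longitudinal model

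*Combined protocol and SAP*

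**What the plan says.** **Objective.** Section 3.3 sets out to explore kidney and vascular endothelial function, "assessed by a panel of molecular markers over the observation period".

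**Markers.** The synopsis, under Other assessments, names SAH and SAM, then seven endothelial markers: "symmetric and asymmetric dimethyl arginine (SDMA, ADMA), L-arginine, L-citrulline, L-ornithine, cysteine, and homocysteine over the observation period". It adds "Plasma concentrations of bioactive lipids (HODEs, HEPEs, HETEs, and prostaglandins) over the observation period" and plasma protein patterns.

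**Sampling.** Table 7-1 has a row headed "Optional sub study: Plasma for Biomarkers". As read from the PDF text it carries 13 marks: screening, Day 3, Days 6 and 7, Week 2, and Months 1, 2, 3, 6, 12, 18, 24 and 36. Note 1 limits Days 5 to 7 with the words "If still inpatient". Note 4 reads "Plasma for biomarkers will be assessed at the University of Colorado in a subset of patients using existing plasma samples". The size of the subset is not given.

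**Analysis.** The synopsis, under Data analysis, states "All continuous variables such as serum creatinine, cGFR, serum lipids, WBC, platelets, etcetera will be compared by student's t test". Sections 10.1.2 and 10.2.1 give "continuous variables by Student's T-Test, non-parametric outcomes will be assessed by Wilcoxon rank sum test (Mann-Whitney U test". Section 10 has no analysis for the exploratory objective. No section names a marker time point, a per-patient summary, a baseline adjustment, a repeated-measures model or a multiplicity rule.

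**The concern.** A t-test or a rank-sum test compares two groups with one independent value per patient. The markers have up to 12 post-transplant values per patient, so the analyst must still decide what to test, and could do so after seeing the data.

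Two obvious choices are poor. Testing each visit separately gives one test per marker per visit, with no single answer about the whole period. Putting all samples into one test treats repeated values from a patient as if they came from different patients. Neither uses the screening sample.

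At stake is the output of the sub-study, a shortlist of markers that differ between the drugs. With an open choice of analysis, chance findings could fill that list, and the precision that serial sampling offers could be lost.

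**Working it through.** The documents give no test count, alpha, correlation or error rate for the markers, so there is no plan figure to reproduce.

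**Inputs from the documents**
- Named analytes: SAH, SAM and the seven endothelial markers = 9.
- Post-baseline marks in Table 7-1: 12, of which Days 6 and 7 are inpatient-only, leaving 10 unconditional.
- Allocation 2:1, with at most 60 patients.

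**Assumptions**
- Two-sided alpha 0.05.
- Within-patient correlation ρ of 0.3 to 0.7, either equal between all visits or decaying by visit as AR(1).
- No true difference between the drugs.

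**1. Visit by visit: number of tests**
- 9 × 12 = 108 tests; 108 × 0.05 = 5.4 expected false positives.
- 9 × 10 = 90 tests; 90 × 0.05 = 4.5.
- These expectations do not depend on correlation. Counting each of the four lipid classes as one further marker gives 13 × 12 = 156 tests.

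**2. Visit by visit: one null marker, 12 visits (8,000 simulated trials)**

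Chance that at least one visit is significant, for ρ = 0.3, 0.5, 0.7:
- Equal correlation: 41%, 31%, 23%.
- AR(1): 45%, 41%, 34%.

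**3. All samples pooled as independent, m = 12**

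The true variance of the contrast is 1 + (m − 1)ρ times the variance that the test assumes. Type I error = 2 × [1 − Φ(1.96 / √(1 + 11ρ))].

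| ρ | 1 + 11ρ | Type I error |
|---|---|---|
| 0.3 | 4.3 | 34.5% |
| 0.5 | 6.5 | 44.2% |
| 0.7 | 8.7 | 50.6% |

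- Simulation (20,000 trials, 2:1) agreed: 34.9%, 44.8% and 51.6% with 60 patients, and 35.4%, 45.5% and 53.4% with 15. The unknown subset size therefore matters little.
- AR(1), 60 patients: 13.6%, 23.2%, 35.1%.
- With only the 10 unconditional visits and equal correlation: 30.8% to 46.8%.

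**4. One average per patient**
- Simulated type I error of a t-test on the per-patient mean: 4.7–5.2% in every setting tried.
- For the nine analytes, 9 × 0.05 = 0.45 expected false positives. The chance of at least one is 1 − 0.95⁹ = 37.0% if the tests are independent and unadjusted.
- Variance relative to one visit is (1 + 11ρ)/12 = 0.358, 0.542, 0.725. The square roots are 0.60, 0.74, 0.85, so the standard error is 40%, 26% and 15% smaller for ρ = 0.3, 0.5, 0.7.

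**5. Adjusting for screening**

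Let ρ_b be the correlation between the screening value and each later value. The relative variance becomes (1 + 11ρ)/12 − ρ_b².
- If ρ_b = 0.2: ρ = 0.3 gives 0.358 − 0.04 = 0.318 (44% smaller standard error). ρ = 0.7 gives 0.725 − 0.04 = 0.685 (17% smaller).
- If ρ_b = ρ: 0.268, 0.292, 0.235, which is 48%, 46% and 52% smaller.

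**The case against.** The strongest reply is that the plan does not choose a wrong method. It leaves an optional exploratory analysis unspecified. Much of that stands.

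- **A t-test can be valid here.** Applied to one named visit, or to one summary per patient, it keeps its 5% level, as step 4 shows. The defect is the missing definition, not the t-test. However, a single visit would not answer a question about the whole period. The plan does give visits for other continuous measures (estimated GFR at 6 months and 1, 2 and 3 years; lipid panels at 1 year) but none for these markers.
- **Neither poor analysis is prescribed.** A reader might infer that the plan commits itself to about 100 tests, or to a pooled test with a 35–51% false-positive rate. The documents support neither. That range needs a pooled analysis that the plan never proposes, and equal correlation from Day 3 to Month 36. Visit-by-visit tests also keep 5% each, so their problem is multiplicity and the lack of one answer.
- **The t-test is not the only stated method.** The rank-sum test is there too, but it does not address repeated values either.
- **Chance findings need not be near certain.** A reader might infer this from the 99.6% chance of at least one false positive among 108 independent tests. If analytes correlate 0.7 with each other, simulation gives 68–90%, and only if every visit is tested.
- **A 46–52% precision gain is not established.** It requires the pre-transplant sample to predict post-transplant levels as well as those predict each other. A new kidney is implanted in between.
- **Thirteen marks are a maximum.** The assays use stored plasma from a subset. Column positions in the extracted table are also uncertain: the follow-up biopsy mark falls under Month 18, while the text below the table says month 12.

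Exploratory status excuses low power and light multiplicity control. It does not excuse leaving open what is compared.

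**Conclusion.** The concern holds as a gap in specification. Serial markers meant to describe the whole follow-up are covered only by two-sample tests, with no stated value per patient to put into them.

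The test counts follow from Table 7-1 and an assumed alpha of 0.05. The pooled error rates depend on the assumed correlation structure: about 35–51% with equal correlation, about 14–35% if it decays. Both are consequences that the wording permits, not properties of the plan. The 15–40% precision gain assumes equal correlation. Any further gain from the screening value depends on an unknown correlation.

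Severity is low. The sub-study is optional, section 3.2 calls all objectives exploratory, and no power is claimed.

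**What to change.** Add a short paragraph on the exploratory objective to section 10, replacing the plain t-test for serial markers:

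- One pre-named contrast per marker: the average post-baseline log concentration, Zortress against Rapamune, adjusted for the log screening value and reported as a ratio with 95% CI.
- ANCOVA on the per-patient mean, or a mixed model with patient as random effect if the subset is large enough to support it.
- A list of the visits that enter the average, and how the inpatient-only Days 6 and 7 are treated. An equal average from Day 3 to Month 36 mixes the perioperative and stable periods, so the choice should be deliberate.
- Visit-specific comparisons reported as descriptive.
- False discovery rate control across markers is optional, given the exploratory status.

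The cost is some wording and slightly more analysis work, within SPSS or STATA as already named. No samples, visits or patients change. The downside is that fewer markers will be reported as nominally significant.

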5.2 Exclusion criteria

- Exclusion Criteria at the time of enrollment:
 - Total cholesterol > 300 mg/dl or triglycerides > 400 mg/dl despite lipid lowering therapy
 - Pre-existing bone marrow suppression (WBC < 3000, platelets < 100,000)
 - Positive crossmatch or ABO incompatible

- Pregnant or nursing (lactating) women, where pregnancy is defined as the state of a female after conception and until the termination of gestation, confirmed by a positive serum human chorionic gonadotrophin laboratory test (>5 mIU/mL)
- Women of child-bearing potential, defined as all women physiologically capable of becoming pregnant, including women whose career, lifestyle, or sexual orientation precludes intercourse with a male partner and women whose partners have been sterilized by vasectomy or other means, UNLESS they are using two birth control methods. The two methods can be a double barrier method or a barrier method plus a hormonal method.
 - Adequate barrier methods of contraception include: diaphragm, condom (by the partner), intrauterine device (copper or hormonal), sponge or spermicide. Hormonal contraceptives include any marketed contraceptive agent that includes an estrogen and/or a progestational agent.
 - Reliable contraception should be maintained throughout the study and for 12 weeks after study drug discontinuation.
 - Women are considered post-menopausal and not of child bearing potential if they have had 12 months of natural (spontaneous) amenorrhea with an appropriate clinical profile (e.g. age appropriate, history of vasomotor symptoms) or six months of spontaneous amenorrhea with serum FSH levels > 40 mIU/mL and estradiol < 20 pg/mL] or have had surgical bilateral oophorectomy (with or without hysterectomy) at least six weeks ago. In the case of oophorectomy alone, only when the reproductive status of the woman has been confirmed by follow up hormone level assessment is she considered not of child bearing potential.
- Active infection (HBV, HIV)
- Malignancy (except for adequately treated squamous or basal cell skin carcinoma) unless patient has written clearance from an Oncologist or if patient has had no malignancy for at least 2 years prior to the transplant
- Allergy or intolerance to sirolimus, everolimus, cyclosporine, or ATG

6 Treatment

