6.5.5 Study drug discontinuation and premature patient withdrawal

As we currently do for Sirolimus, Zortress dosing will be decreased or discontinued when the transplant physician deems appropriate due to deleterious side effects or the presence of infection or malignancy where a reduction in overall immunosuppression is desirable.

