8.1 Adverse events

Adverse events that the investigators consider to be clinically significant and associated with the use of Zortress® or Rapamune® will be recorded at each study visit. Serious adverse events will be reported to Novartis within 24 hours of discovery or notification. An adverse event will be considered serious if it results in any of the following outcomes:

- Results in death,
- Is life threatening (an adverse event is considered “life-threatening: if, in the view of the investigator, its occurrence places the subject at immediate risk of death. It does not include an adverse event that, had it occurred in a more severe form, might have caused death),
- Results in persistent or significant disability/incapacity, or substantial disruption of the ability to conduct normal life functions,
- Results in congenital anomaly, or birth defect,
- Requires inpatient hospitalization or leads to prolongation of hospitalization (hospitalization for treatment/observation/examination caused by AE is to be considered as serious).
- Other medically important events

Follow-up information for serious adverse events will be collected, recorded, and reported to Novartis.

Adverse events that meet IRB reporting requirements will be submitted to the IRB for review.

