8.2 Serious adverse event reporting

To ensure patient safety, every SAE, regardless of suspected causality, occurring after the patient has provided informed consent and until 30 days after the patient has stopped study participation (defined as time of last dose of study drug taken or last visit whichever is later).

Any SAEs experienced after this 30 day period should only be reported to Novartis if the investigator suspects a causal relationship to the study drug.

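### No incidence or lowest-count analysis of cytopenia is planned; the only analysis naming WBC or platelets is a t-test with no stated timepoint or summary

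*Combined protocol and SAP*

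**What the plan says.** - **Analysis.** Synopsis, Data analysis: "All continuous variables such as serum creatinine, cGFR, serum lipids, WBC, platelets, etcetera will be compared by student's t test". The next sentence adds a general rule: "Any other dichotomous variables will be compared by chi squared analysis". Sections 10.1.2 and 10.2.1 repeat the t-test and chi-squared assignments by type of variable and add that "non-parametric outcomes will be assessed by Wilcoxon rank sum test (Mann-Whitney U test").
- **Measurement.** The synopsis and section 4 list "bone marrow function (WBC and platelet count") among the standard-of-care laboratory tests. Table 7-1 schedules hematology at 13 visits; after month 3 these are months 6, 12, 18, 24 and 36.
- **Cut-offs.** Section 5.2 excludes "Pre-existing bone marrow suppression (WBC < 3000, platelets < 100,000"). These figures are used nowhere else. The synopsis also has Thymoglobulin adjusted for both counts.
- **Endpoints.** Low counts appear in none of the secondary objectives (3.2), the synopsis list of other assessments, the secondary endpoints (10.1.2, 10.2.1) or the safety descriptions (10.1.2, 10.2.2).
- **Other routes.** Section 8.1 records "Adverse events that the investigators consider to be clinically significant and associated with the use of" either mTOR drug. Section 8.2 covers "every SAE, regardless of suspected causality, occurring after the patient has provided informed consent". Section 6.5.4 records all dose adjustments and interruptions, 10.2.1 makes the reason for a drug switch an endpoint, and 10.2.2 reviews admissions monthly.

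**The concern.** The protocol treats marrow suppression as a patient-level event with a threshold when it decides who may enter, but names only a comparison of continuous values when it looks for the harm afterwards. Other harms in the synopsis (wound infection, lymphocele, viral infection, MI and CHF) are listed as incidences.

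A low count in a minority of patients moves an arm mean very little, and less still if the count is back up at the analysed visit. Section 6.5.5 makes recovery possible, since "Zortress dosing will be decreased or discontinued when the transplant physician deems appropriate due to deleterious side effects". Two arms could then differ in how many patients were ever cytopenic while their mean counts look alike. What is at stake is the second aim in section 1: describing how the side effects of Zortress differ from those of Rapamune.

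**Working it through.** **No figure to reproduce.** The documents give no alpha, SD, cytopenia rate or power, and section 10.3 says the study is not powered. From the documents: 60 patients randomized 2:1, so 60 × 2/3 = 40 Zortress and 60 × 1/3 = 20 sirolimus. Everything else below is assumed.

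**1. What a t-test can see.** At two-sided alpha 0.05 and 80% power, the detectable difference is (1.96 + 0.84) × √(1/20 + 1/40) = 0.77 SD.

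**2. What cytopenia does to one visit's mean.** Assume WBC (×10³) with mean 6.5 and SD 2.0, floored at 3.0 in unaffected patients (mean after flooring 6.53). Affected patients are uniform on 1.5 to 3.0 (mean 2.25). Ever-low rates are 5% and 25%.
- All affected patients still low: gap = 0.20 × (6.53 − 2.25) = 0.86. Simulated t-test power is 28% to 30% with the excess in the 20-patient arm.
- One in five still low: gap = 0.20 × 0.86 = 0.17. The standard error is about 2.0 × √(1/20 + 1/40) = 0.55, so the gap is about 0.31 standard errors. Simulated power is 6% to 7% with the excess in the 20-patient arm and 5% to 6% with it in the 40-patient arm, close to the false-positive rate.

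**3. What an ever-low comparison would see.** Exact power of Fisher's test, by enumeration:

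| Ever-low rates | Excess in the 20-patient arm | Excess in the 40-patient arm |
|---|---|---|
| 5% v 25% | 58% | 46% |
| 10% v 30% | 44% | 37% |

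**4. A second model.** Assume 13 visits, between-patient SD 1.2, within-patient SD 1.0, one or two low visits per affected patient, and rates of 10% (20-patient arm) v 30% (40-patient arm). The overall mean moves by 0.07 to 0.13. Rejection rates are about 5% for a t-test at one late visit, 5% to 7% for a t-test on patient means, 23% to 24% for a t-test on each patient's lowest count, and about 41% for chi-squared on ever below 3000.

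**5. Would a scheduled visit catch an episode?** Assume visits at days 14, 30, 61, 91, 183 and 365, and an episode of 14 or 28 days with uniform onset. The probability is the number of onset days that reach a visit divided by the length of the onset window.
- Onset days 14 to 365: 70/351 = 0.20 to 128/351 = 0.36.
- Onset days 14 to 183: 56/169 = 0.33 to 100/169 = 0.59.
- Onset days 14 to 91: 42/77 = 0.55 to 72/77 = 0.94.

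The answer depends on when episodes start, which the documents do not say.

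**The case against.** A reader might infer that marrow suppression is assessed solely through mean counts and that the harm could go unreported. The documents do not support that.
- A serious event is covered whatever its cause (8.2), and hospitalization makes an event serious (8.1).
- A switch of drug is an endpoint with its reason (10.2.1), dose changes are recorded (6.5.4), and admissions are reviewed monthly (10.2.2).
- The general chi-squared rule would apply to a yes/no cytopenia variable if one were defined, and a t-test on each patient's lowest count would fit the synopsis wording.

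A reader might also infer that low counts have usually recovered by the next visit. No section says so: 6.5.5 mentions neither recovery nor cytopenia, and standard-of-care results add to the Table 7-1 visits.

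Further, this is an exploratory pilot, the rates are assumed, an incidence comparison is itself weak at 40 v 20, and the cut-offs are entry criteria rather than toxicity definitions.

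All of this stands, and it narrows the point. It does not remove it. Recording under 8.1 depends on the judgement of unblinded investigators; dose changes are recorded, but no comparison by arm is specified; a patient managed by dose reduction has no switch to explain; and a Wilcoxon test at a single visit also misses recovered episodes. The general rules name no cytopenia variable, so threshold, window and summary would be chosen after open-label data are in view.

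**Conclusion.** The point holds in a limited form. Neither the incidence of low counts nor the lowest count is prespecified, the one named analysis has no timepoint or summary, and no tabulation by arm is planned. The gap concerns transient, non-serious cytopenia that causes no switch and is not judged both clinically significant and drug-associated.

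The contrast of about 6% for the t-test with 46% to 58% for Fisher's test at 5% v 25% rests on assumed rates, an assumed SD and one in five patients still low. It shows that a mean is the wrong summary, not how often the harm occurs. At 10% v 30% Fisher's 37% to 44% is still low, so the gain is in description rather than a dependable test. The effect is on the side-effect profile; the primary endpoint and its conclusion are untouched.

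**What to change.** In section 10.2.1 and the synopsis Data analysis paragraph:
- Add, by arm, the number and proportion of patients with any post-transplant WBC < 3000 and with any platelets < 100,000, by 6 months and by 1 year, each with an exact 95% confidence interval. State that these are the entry cut-offs, used only as descriptive reporting thresholds.
- Take values from all hematology results in the transplant database (section 9.1), not only the Table 7-1 visits.
- Show the induction week separately, because Thymoglobulin is common to both arms.
- Keep the comparison of means as supportive, and state its visit and summary.

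The cost is plan wording and two tables from results already stored. The downside is wide intervals at 40 v 20: 5 of 20 gives 9% to 49%. No dosing or clinical management rule changes.
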